#### Monitoring Prior to Opening Accrual Period 2

The core team, together with the SMC, will review the results of the accrual period 1 interim PK and safety analysis. If the acceptable PK criteria for RBT and LPV are met, and if no more than three participants in each treatment arm report  $\geq$  Grade 3 AEs attributed to study-provided drug(s) by 28 days after ART initiation, and if no more than three participants in each treatment arm discontinue study-provided drug(s) for treatment-limiting toxicity or intolerance (such that PK assessments cannot be completed), then accrual period 2 will open at the planned dose schedules of LPV/r and RBT.

If acceptable PK criteria are not met, or if more than three participants in one or more treatment arms report  $\geq$  Grade 3 AEs attributed to study-provided drug(s) by 28 days after initiation of ART, or if more than three participants in one or more treatment arms discontinue study-provided drug(s) for treatment-limiting toxicity or intolerance (such that

PK assessments cannot be completed), the SMC, in consultation with the core team, may elect to adjust the doses of RBT and/or LPV/r, as described above, for participants in the affected arm identified with inadequate drug concentrations, and repeat steady-state (day 12 ± 2 after dose adjustment) drug concentrations will be obtained for only the study arm participants in which a dose was adjusted (see dose adjustment schedule above). A second accrual period 1 PK and safety interim analysis will be conducted after all accrual period 1 participants undergoing dose adjustment have completed 28 days of dose-adjusted treatment and when day 12 ± 2 post-dose adjustment drug concentrations are available. This second analysis will include all accrual period 1 participants with available data.

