The core team and SMC will then review the results of the second accrual period 1 interim PK and safety analysis. If acceptable PK criteria are not met, or if more than three participants in one or more treatment arms report ≥ Grade 3 AEs attributed to study-provided drug(s) by 28 days after initiation of ART, or if more than three participants in one or more treatment arms discontinue study-provided drug(s) for treatment-limiting toxicity or intolerance (such that PK assessments cannot be completed, then a decision will be made about whether to continue, modify (e.g., add additional participants to the accrual period 1 to assure adequate PK assessment are completed), or halt the treatment arm(s) in question, based on analysis of the nature of the AEs and reasons for study-provided drug discontinuation, and the degree of PK criteria failure. At the second interim review, if three or fewer participants report ≥ Grade 3 AEs attributed to study-provided drug(s) in all treatment arms, and if three or fewer participants in all treatment arms discontinue study-provided drug(s) for treatment-limiting toxicity or intolerance (such that PK assessments cannot be completed), and acceptable PK criteria are met for at least two of the treatment arms, the SMC, in consultation with the core team, will determine whether accrual period 2 will open.

If, based on the SMC's determination, unacceptable PK and/or safety criteria are met within two treatment arms, then further enrollment into the study may be stopped, and accrual period 1 participants will be managed according to best available local TB and ARV treatment. These participants will be followed off study-provided drug (LPV/r, RTV, RAL, and/or RBT) for the remainder of study follow-up (up to 72 weeks).

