### 9.2 Primary Endpoints

#### 9.2.1 Accrual Period 1 PK Study Endpoints

- 9.2.1.1 LPV plasma concentrations at day  $12 \pm 2$  (after initiation of ART) in Arms A, B, and C.
- 9.2.1.2 RBT plasma concentrations at day  $12 \pm 2$  (after initiation of ART) in Arms A and C.
- 9.2.1.3 Grade 3 or 4 laboratory value or sign or symptom attributed to study-provided medication(s) by 28 days of ART.

9.2.1.4 Discontinuation of study-provided drug(s) for treatment-limiting toxicity or intolerance (such that PK assessments within the day  $12 \pm 2$  (after initiation of ART) window cannot be completed).

9.2.2 Primary endpoint: HIV virologic suppression is defined as plasma HIV-1 RNA level  $< 400$  copies/mL at 48 weeks.

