The core team and SMC will then review the results of the second accrual period 1 interim PK and safety analysis. If acceptable PK criteria are not met, or if more than three participants in one or more treatment arms report  $\geq$  Grade 3 AEs attributed to study-provided drug(s) by 28 days of ART, or if more than three participants in one or more treatment arms discontinue study-provided drug(s) for treatment-limiting toxicity or intolerance (such that PK assessments cannot be completed), then a decision will be made about whether to continue, modify (e.g., add additional participants in the accrual period 1 to assure adequate PK assessment are completed), or halt the treatment arm(s) in question, based on analysis of the nature of the AEs and reasons for study-provided drug discontinuation, and the degree of PK criteria failure. At this second interim review, if three or fewer participants report  $\geq$  Grade 3 AEs attributed to study-provided drug(s), and if three or fewer participants discontinue study-provided drug(s) for treatment-limiting toxicity or intolerance (such that PK assessments cannot be completed), and if acceptable PK criteria are met for at least two of the treatment arms, the SMC, in consultation with the core team, will determine whether accrual period 2 will open.

If, based on the SMC's determination, unacceptable PK and/or safety criteria are met within two treatment arms, then further enrollment into the study may be stopped, and accrual period 1 participants will be managed according to best available local TB and ARV treatment. These participants will be followed off study drug for the remainder of study follow-up (up to 72 weeks).

If the SMC determines that accrual period 2 enrollment should proceed, accrual period 2 participants will then be randomized 1:1:1 to Arm A, B, or C (or with

equal probability to the remaining sample size in the remaining treatment arms) at the doses determined during the dose-finding period in accrual period 1 participants. No individual dose adjustments will be made based on drug concentrations for participants enrolled during the accrual period 2.

Based on this monitoring, if criteria are determined to be unacceptable in any treatment arm before the three accrual period 1 cohorts are fully enrolled, further accrual to the arm in question may be stopped.

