### **1.5.2 Safety Criteria**

- 1) No more than three participants in any treatment arm experience a Grade 3 or Grade 4 AE “related to study-provided drug(s)” (as deemed by the TDM Team: DAIDS Clinical Representative, Protocol Co-Chairs, Protocol Vice Chair, Protocol Pharmacologist, Statisticians, Data Manager, Laboratory Data Manager, and Clinical Trials Specialist) by 28 days after initiation of study-provided ART and TB medications.
- 2) No more than three participants in any treatment arm discontinue study-provided drug(s) for treatment-limiting toxicity or intolerance (such that PK assessments within the day  $12 \pm 2$  [after initiation of study-provided ART and TB medications] window cannot be completed).

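### At the second accrual period 1 review, the adverse-event fail trigger is timed from ART start rather than from the dose adjustment, and it disagrees with the go condition, which states no window

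*Protocol*

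**What the plan says.** Protocol 3.0 (Monitoring Prior to Opening Accrual Period 2) and Protocol 9.5.1 describe the same two-step process.

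- **Timing of the second review.** It is held "after all accrual period 1 participants undergoing dose adjustment have completed 28 days of dose-adjusted treatment". The repeat drug concentrations are taken 12 ± 2 days after the adjustment. The analysis takes in all accrual period 1 participants with data.
- **Fail trigger at the second review.** In 3.0 an arm is in question if more than three participants have at least "Grade 3 AEs attributed to study-provided drug(s) by 28 days after initiation of ART". In 9.5.1 the wording is "Grade 3 AEs attributed to study-provided drug(s) by 28 days of ART".
- **Go condition at the second review.** In 3.0 three or fewer participants may report at least "Grade 3 AEs attributed to study-provided drug(s) in all treatment arms". In 9.5.1 it begins "At this second interim review, if three or fewer participants report". Neither sentence gives a time window for these events.
- **Definitions.** The accrual period 1 safety endpoint (Protocol 9.2.1.3) is a Grade 3 or 4 event "attributed to study-provided medication(s) by 28 days of ART". The criteria in 9.5.1 and 9.6.1 also start the clock at ART. SAP 1.5.2 counts events "by 28 days after initiation of study-provided ART and TB medications". No section defines an adverse-event window that starts at the dose adjustment.

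**The concern.** The second review decides whether an adjusted dose can go into accrual period 2 (n=411, Protocol 9.4.3), where dosing follows the final accrual period 1 dose (5.1.2) and no individual adjustment on concentrations is made. Protocol 9.6.2 itself allows that participants whose dose was adjusted might have greater toxicity. The timing of the review and the repeat PK were both moved to the adjustment, but the clock in the adverse-event fail trigger was not. That count can therefore be settled before the adjusted dose is taken. The go condition, with no window, can give a different answer on the same data.

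**Working it through.** **1. The plan's own figure.** Table 9.2 gives the probability of at most 3 events in 20 participants. At a 10% rate:

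P(X ≤ 3) = Σ C(20,x) · 0.10^x · 0.90^(20−x), x = 0 to 3, = 0.867.

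This matches the 87% in Protocol 9.5.1, and all 25 cells of the table reproduce to within 0.001. The table is sound. The question is which days feed the count.

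**2. Which days are counted.** The full review waits until 54-60 of the 60 participants have completed 28 days of ART. For a participant who has done so, an adjustment made at or after that review starts after day 28. The overlap between the adjusted-dose days and the counted days is then 0 of 28. At most 60 − 54 = 6 participants could still be inside their window. Setting those aside:

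- an arm with four or more counted participants at the first review still has four or more, because the same events are counted again;
- an arm with three or fewer, which failed only on PK, keeps that count whatever happens on the adjusted dose.

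**3. Adjustments before the full review.** Day 12 ± 2 PK falls on days 10-14, samples ship every 14 days, and the laboratory reports within 14 days. Results could come at about day 10 with no waiting, or at 14 + 14 + 14 = day 42. Protocol 10.2.3 allows a missed-dose PK study to be repeated up to 12 days after its scheduled date, giving 14 + 12 + 14 + 14 = day 54. Transit and the weekly review come on top. Some early-adjusted exposure can therefore fall inside day 28. New participants started on an adjusted dose after the early interim review have all of their first 28 ART days on that dose counted.

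**4. Size, as an illustration.** Assumed: rate p1 = 10% in the first 28 days of ART; all 20 in the arm adjusted after day 28; rate p2 in the 28 days after adjustment; the two windows independent. Counting both windows uses p = 1 − (1 − p1)(1 − p2); for p2 = 25%, p = 1 − 0.90 × 0.75 = 0.325.

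| p2 | Trigger as written, P(≤ 3) | 28 days from adjustment, P(≤ 3) | Both windows, P(≤ 3) |
|---|---|---|---|
| 10% | 0.867 | 0.867 | 0.456 |
| 20% | 0.867 | 0.411 | 0.147 |
| 25% | 0.867 | 0.225 | 0.070 |
| 40% | 0.867 | 0.016 | 0.004 |

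The second column does not respond to p2.

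**5. The gap between the two sentences.** If the go condition is read as cumulative, an arm with three or fewer events by day 28 can exceed three in total. It then meets neither the adverse-event fail trigger nor the adverse-event go condition. Under the same assumptions the probability, given three or fewer by day 28, is 1 − 0.456/0.867 = 0.47 at p2 = 10% and 1 − 0.070/0.867 = 0.92 at p2 = 25%.

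**6. Whether the limit of three can be carried over.** After the full review only participants with inadequate concentrations are adjusted. If 5 are adjusted (assumed), P(X ≤ 3) = 1 − (5 + 1)/32 = 0.81 even at a 50% rate, and 0.984 at 25%. Taken as a proportion, 3/20 = 15% of 5 is 0.75, which permits no events. Neither version carries over.

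**The case against.** A reader might infer that the second review ignores the adjusted dose altogether. The documents do not support that. The go sentences have no time limit and, read literally, include adjusted-dose events. Early-adjusted participants and new participants started on an adjusted dose contribute inside the ART window. The core team also sees adverse-event reports weekly until the final SMC review.

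A reader might also infer that the rule automatically clears or blocks a dose. It does not. Meeting the criteria at the second review leaves the SMC to determine whether accrual period 2 opens. Failing leads to a choice to continue, modify or halt, with the nature of the events weighed. An arm with four carried-over participants can continue. This stands, and it limits the consequence. However, weighing the nature of the events is written only for an arm that has failed a criterion, so it is not tied to the case where the trigger stays silent.

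The discontinuation limit could be said to fill the gap, since at the second review it refers to PK that could not be completed and the new PK follows the adjustment. But Protocol 9.2.1.4 and the criteria in 9.5.1 tie it to the window after ART start. Even on the generous reading, stopping after the repeat PK would not count. It is ambiguous rather than absent.

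SAP 1.5.2 does not confirm an error at the second review. That plan covers the full interim analysis, where a treatment-start window is appropriate, and it plans no second review. SAP 4.1 tabulates events beyond 28 days but ties only the first-28-day table to the criterion. SAP 1.6 also states that accrual period 2 will not open.

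**Conclusion.** The point holds in a limited form. For participants adjusted at the full review, the adverse-event fail trigger reflects mainly the original dose, and the fail and go sentences at the same review disagree. That an arm over three must meet the trigger again, and that an arm failing only on PK cannot meet it through adjusted-dose toxicity, follows from the text, apart from the few participants still within 28 days of ART. The probabilities (0.867 regardless of the adjusted dose, against 0.225 at a 25% rate counted from the adjustment) rest on the assumed 10% first-window rate, all 20 adjusted after day 28, and independence. They show how insensitive the trigger is and do not predict what would happen to an arm. SMC discretion limits the effect, and because accrual period 2 will not open, practical urgency is low. The defect is in the protocol as written and would matter if a second review were held or the design reused.

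**What to change.** Reconcile the second-review text in Protocol 3.0 and 9.5.1, and add a matching definition beside those in 9.2.1 and 9.6.1:

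- In adjusted participants, count attributable Grade 3 or higher events, and discontinuations for toxicity or intolerance, over the 28 days from the first adjusted dose.
- Give this group its own denominator, and use the same window in both the fail and the go sentence.
- Report the original-dose counts separately, as the result of the first review.
- Have the sponsor set the limit from the actual number adjusted, with operating characteristics laid out as in Table 9.2, rather than carry over 3 of 20.

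This takes no position on any dose. The cost is a few sentences in those four sections, a small probability table and an extra set of columns in the safety table. Drug modifications and Grade 3 or higher events are already recorded (Protocol 6.3.5 and 6.3.9). The drawback is that the adjusted group may be small, so its rate will be imprecise and any limit will discriminate weakly. That should be stated alongside the limit.

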#### 4.0 SELECTION AND ENROLLMENT OF PARTICIPANTS

##### 4.1 Inclusion Criteria

4.1.1 HIV-1 infection, documented by any licensed rapid HIV test or HIV enzyme or chemiluminescence immunoassay (E/CIA) test kit at any time prior to study entry and confirmed by a licensed Western blot or a second antibody test by a method other than the initial rapid HIV and/or E/CIA, or by HIV-1 p24 antigen, plasma HIV-1 RNA viral load.

NOTE: The term “licensed” refers to a US FDA-approved kit, which is required for all IND studies, or for sites located in countries other than the US, a kit that has been certified or licensed by an oversight body within that country and validated internally. Non-US sites are encouraged to use US FDA-approved methods for IND studies.

WHO and the US Centers for Disease Control and Prevention (CDC) guidelines mandate that confirmation of the initial test result must use a test that is different from the one used for the initial assessment. A reactive initial rapid test should be confirmed by either another type of rapid assay or an E/CIA that is based on a different antigen preparation and/or different test principle (e.g., indirect versus competitive), or a Western blot, plasma HIV-1 RNA viral load, or an HIV-1 p24 antigen test.

4.1.2 CD4+/CD8+ T-cell count obtained within 30 days prior to study entry at any laboratory that has a CLIA certification or any Division of AIDS (DAIDS) approved laboratory.

4.1.3 Confirmed or probable pulmonary or extrapulmonary TB, as defined below.

Confirmed pulmonary TB is defined as the presence of compatible clinical symptoms (e.g., cough, hemoptysis, shortness of breath, chest pain, weight loss, fever, or night sweats) with or without abnormal chest X-ray, chest computed tomography [CT] scan or other chest imaging (e.g., hilar lymphadenopathy, paratracheal lymphadenopathy, alveolar consolidation, miliary pattern, lung parenchymal breakdown/cavitation, or Ghon focus) and sputum, bronchial alveolar lavage fluid, pleural fluid, pleural tissue, lung tissue, or gastric acid lavage culture positive for MTB, or a nucleic acid amplification test positive for MTB or MTB Complex.

Confirmed extrapulmonary TB is defined as the presence of compatible clinical symptoms as previously described plus clinical features of organs involved, such as sterile pyuria or other renal involvement, pericarditis, ascites, pleural effusion, meningitis, arthritis, orchitis, enteritis, extrathoracic lymphadenitis, or osteitis and positive culture for MTB or nucleic acid amplification test positive for MTB or MTB Complex from fluid or tissue biopsies from any of these organ or tissue sites, including bone marrow, liver, and blood.

Probable Pulmonary TB is based on the clinician's judgment and includes compatible clinical symptoms as previously described, and at least one of the following: 1) positive sputum smear for acid fast bacilli (AFB); or 2) abnormal CXR, chest CT scan or other chest imaging; or 3) evidence of granulomata with organisms positive for AFB or caseating granulomata on lung tissue biopsy; or 4) positive tuberculin skin test (TST) ( $\geq$  5mm) or interferon gamma release assay (IGRA); and without concurrent illness that would explain the findings, but MTB cultures are negative or not available.

Probable Extrapulmonary TB is based on the clinician's judgment and includes compatible clinical symptoms as previously described plus clinical features of organs involved as previously described, or evidence of granulomata with organisms positive for AFB or caseating granulomata on tissue biopsy from relevant site(s); and specific antituberculous therapy initiated or recommended, but MTB cultures are negative or not available.

NOTE: Participants whose qualifying episode of TB was later determined not to be TB will continue to be followed on study but off study drugs for safety and ART endpoints.

- 4.1.4 Chest x-ray within 30 days prior to study entry.
- 4.1.5 A PI-based ART regimen is required, as determined by the participant's primary clinician/clinical facility.

NOTE: Enter the reason, in the eligibility checklist, for the PI-based ART regimen from among the following choices:

The PI-based therapy was required:

- 1) Because the participant failed an NNRTI regimen or;
- 2) Because the participant had an adverse reaction to an NNRTI regimen or;
- 3) Because the participant received single dose nevirapine during pregnancy and could have NNRTI resistance mutations archived at the time the participant was starting ART;
- 4) Other, specify.

4.1.6 Laboratory values obtained within 14 days prior to study entry:

Accrual period 1

- Absolute neutrophil count (ANC)  $\geq 750$  cells/mm^3
- Hemoglobin  $\geq 8.5$  g/dL
- Platelet count  $\geq 50,000/\text{mm}^3$
- Alanine aminotransferase (ALT) (SGPT)  $\leq 2 \times$  upper limit of normal (ULN)
- Aspartate aminotransferase (AST) (SGOT)  $\leq 5 \times$  ULN
- Total bilirubin  $\leq 2.5 \times$  ULN

Accrual period 2

- ANC  $\geq 500$  cells/mm^3
- Hemoglobin  $\geq 7.5$  g/dL
- Platelet count  $\geq 50,000/\text{mm}^3$
- AST (SGOT) and ALT (SGPT)  $\leq 5 \times$  ULN
- Total bilirubin  $\leq 5 \times$  ULN

4.1.7 For females of reproductive potential, negative serum or urine pregnancy test within 7 days prior to study entry and 72 hours of starting study medications.

NOTE: Female participants of reproductive potential are defined as women who have reached menarche or who have not been post-menopausal for at least 24 consecutive months (i.e., who have had menses within the preceding 24 months) or have not undergone surgical sterilization (e.g., hysterectomy, or bilateral oophorectomy or salpingectomy).

4.1.8 All participants must agree not to participate in a conception process (e.g., active attempt to become pregnant or to impregnate, donate sperm, or in vitro fertilization).

4.1.9 Female participants who are participating in sexual activity that could lead to pregnancy must agree to use at least two reliable methods of contraception: a barrier method of contraception (condoms or cervical cap) together with another reliable form of contraception (condoms, with a spermicidal agent; a diaphragm or cervical cap with spermicide; an IUD; or hormone-based contraceptive) while receiving RIF, or other rifamycin, and for 6 weeks after stopping these drugs.

- Female participants who are not of reproductive potential, as defined above, or whose male partner(s) have undergone successful vasectomy with documented azoospermia or have documented azoospermia for any other

reason, are eligible without requiring the use of contraceptives. Participant-reported history is acceptable documentation of menopause, hysterectomy, or bilateral oophorectomy or salpingectomy.

- 4.1.10 Karnofsky performance score > 40 within 14 days prior to study entry, and likelihood of survival, in the opinion of the site investigator, for at least 6 months.
- 4.1.11 Men and women  $\geq 18$  years of age, who have attained the minimum age of consent, as defined by the local IRB.
- 4.1.12 Ability to swallow oral medications.
- 4.1.13 Ability and willingness of participant or legal guardian/representative to provide informed consent.

